## **8.0 STUDY PROCEDURES**

After signing informed consent, participants will complete approximately 4 study visits. The study will enroll 250 completers (and 5 Urology provider-participants). Data collected will include demographics, medical history, laboratory values pre, and post-operative procedure, medications, and treatment history. Data collected from the Urology provider-participants will include information from the provider-participant questionnaire. The following procedures will be completed:

### **8.1 Enrollment (research)**

After shared decision making with their physician, if patients have elected to undergo a urologic stone procedure that will require transurethral surgery and access to the urinary system, the study team will be alerted. After screening the chart to confirm inclusion and exclusion criteria are met, the approved study team will approach for enrollment and engage in informed consent process.

## **8.2 Urine Collection (standard of care)**

Approximately 30-50 mL of whole urine will be collected for a standard of care urine culture corresponding to the patients' pre-operative visit. Approximately 5-10 mL of left-over urine will be obtained for research and sent to MicroGen Dx, a CAP-accredited and CLIA licensed clinical diagnostic lab, for analysis. Urine will be collected by research staff, placed in collection containers supplied by MicroGen Dx and labeled with unique subject ID. De-identified samples will be sent to MicroGen Dx in accordance with their guidelines. In the event, the urine culture was performed more than 45 days before the urologic procedure; the treating physician will ask the patient to provide an additional urine sample. Research staff will obtain an additional 5-10 mL of urine, which will then be sent to MicroGen Dx for analysis.

### **8.2a Urinary Stone Analysis**

During the patients' surgical procedure, the treating physician will remove the stone (s) and send to a laboratory/pathologist for analysis as part of routine care. The removed stone specimens are diluted in a saline solution, and the laboratory will analyze for the stone's chemical composition. Any extra or leftover stone (s) available that will not be sent for routine analysis will be sent to MicroGen DX for analysis and bacteria detection. Urinary stone analysis completed by MicroGen DX will be done only for a proportion of the samples (n=20). Samples will be de-identified with the same study ID as the subject's research urine sample.

## **8.3 Medical History/Demographics (research)**

Data collected will include demographics, medical history, to include but not limited to, medication and treatment history, laboratory and vitals results, diagnosis results, and procedure and surgical history.

## **8.4 Randomization (research)**

A randomization list will be generated using a computer-based-random number generator [www.randomizer.org](http://www.randomizer.org). Randomization will be created 1:1, n=110 per group. Once created, individual envelopes will be created, and study staff will pull an envelope after the participant signs consent. The research staff will not be blinded to the randomization groups. The standard of care group will have urine culture results directed to treating physician. The intervention group will have NGS results sent to Infectious Disease pharmacist, [name] to provide an antibiotic recommendation. The antibiotic recommendation, along with NGS results, will then be provided to treating physician. The physician will then utilize these tools to select the best antibiotic for the case but is not required to abide by the ID pharmacist's recommendation. The standard of care group will have a urine sample sent to MicroGen Dx, but the results will not be provided to the physician.

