Ureteroscopy for urinary tract urolithiasis is a common procedure with an estimated 9,200 cases in the US per year. However, the incidence of systemic inflammatory response syndrome (SIRS) after flexible ureteroscopic (URS) lithotripsy is 7.1%, despite the use of recommended antibiotic prophylaxis. Obtaining a urine culture prior to surgery is standard of care, and physicians start culture-specific antibiotic treatment on patients with a positive culture—and preferably found to be negative on repeat culture—before their urologic stone procedure. One of the challenges when choosing a prophylactic agent is that preoperative urine cultures often show no growth for patients who later develop SIRS. Singh *et al.* found no significant association between pelvic urine cultures or stone cultures and the occurrence of SIRS. We hypothesize the stone or previously placed stent may allow bacteria to form biofilms or not detected by standard cultures.

Next Generation Sequencing (NGS) technology could assist physicians in selecting antibiotic prophylaxis therapy before surgery in patients that have a normal urine culture. Urine culture is a technique that utilizes specialized agar to select the bacterial presence in a fluid. Issues with standard culture are that one must use a priori select particular groups of bacteria and assume they would grow on the plate, which requires the bacteria to be at a certain concentration. NGS testing can use the combination of PCR and 16sRNA to identify the bacterial presence and does not discriminate by growth patterns and are not limited by bacterial counts. NGS can also identify fungal species, which require a separate technique when using standard culture. Our proposal focuses on the identification of high-risk cases and antibiotic prophylaxis patterns and how NGS can assist with antibiotic prophylaxis decision making. Anticipating the use of NGS may have unintended consequences, we address issues with implementation and how to establish an interpersonal healthcare approach to abide by antibiotic stewardship programs.

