Infectious complications are the most common cause of death following urologic stone procedures and present a sizeable economic drain on the American healthcare system. Other studies have found that up to 17% of urosepsis cases follow urologic interventions. Koras et al. (2014) observed signs of SIRS in up to 27% of patients who underwent PCNL, 7.6% of which were diagnosed with sepsis. Given the mortality rates and economic costs of urosepsis, SOC practices must be optimized to reduce the risk of infectious complications following urologic procedures.

NGS identifies a targetable bacterium in up to 50% of negative urine cultures prior to urologic stone surgery. Many physicians chose to escalate IV antibiotics rather than utilized oral medications. Therefore, working with an infectious disease pharmacist may be helpful in guiding the selection and operating room availability of

**Figure 2:** Preliminary results from NGS compared to standard urine culture prior to urologic surgery.

antibiotics based on NGS results to improve antibiotic stewardship. Larger long-term studies are needed to determine if this strategy will lead to reduced infection rates.

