Remote Consent/Waiver of documentation of informed consent: Eligible subjects undergoing standard of care visits via telephone, video conference or telemedicine will be consented remotely in the absence of face-to-face contact. The purpose of remote consent is to allow the study investigator/designee and potential subject to engage in the informed consent process similar to what would be conducted face-to-face under normal circumstances. Initially, subjects will be introduced to the study by urology provider and explain the consent process. Subjects will be informed that a consent form will be sent via e-mail, mail or fax. Following delivery of the consent form, approved research staff will call subject and conduct the consent interview via telephone when the subject can read the consent form during the discussion. Research staff will confirm subject's name and date of birth from subject before discussion to ensure the identity of the subject. If agreed to participate, subject will provide verbal consent. No study procedures will occur until the subject and research staff have provided verbal consent.

Each participant will be assigned a unique subject identifier (subject ID) that has no meaning external to the study database. The participant identifiers will be further masked and password protected, and stored only on a secure server behind a "firewall." Only the PI of the IRB approved protocol ([name]) and approved research staff will have access to these identifiers. A research study file will be kept for each participant accrued. This file will include the participant's consent, the assigned unique subject identifier, research records, and copies of relevant source documents. All participant records will be securely stored in the Urology research offices. A data entry system will be prepared in RedCap, Excel, or equivalent software interface for the study. Both the subject identifier and sequence number for each patient will be entered into the database together with clinical outcome data collected across visits.

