### **10.0 METHOD OF ANALYSIS/STATISTICS**

**Next Generation Sequencing:** Standard of care whole urine will be collected (approximately 30-50 mL) utilizing special vacutainers supplied by MicroGen Dx. Approximately 5-10mL of urine taken for culture will be sent to MicroGen Dx, a CAP-accredited and CLIA licensed clinical diagnostic lab, for analysis. MicroGen Dx will perform rapid PCR for common resistance genes prior to ureteroscopy or percutaneous nephrolithotomy. The plan will be to run target bacterial or fungi DNA on the quantitative PCR (qPCR) panel assay on the Roche LightCycler 480 II instrument and sequencing of 16S ribosomal RNA hypervariable regions V1-V2 using Ion Torrent (Ion Torrent PGM).

**Microbiome:** Sequencing reads were demultiplexed using QIIME2 software and denoised using dada2 software, using a phred score threshold of 28. Alpha diversity will be measured using the Shannon index, and a Wilcoxon test was used to determine whether the Shannon index differed between patients with stents and those without stents at the time of urine collection. Principle coordinates analysis (PCoA) of Bray-Curtis dissimilarity will be performed to visualize differences in species composition between patients with and without stents, and Linear discriminant analysis Effect Size (LEfSe) analysis was conducted to identify differentially abundant taxa between stent and non-stent groups.

**Sample size:** This will be a randomized trial of Microgen Dx versus standard of care. The primary endpoint is infection within 14 days of surgery. The primary objective of the study is to evaluate whether Microgen Dx reduces an infection rate compared to the standard of care. The null hypothesis is that infection rates within 14 days of surgery are the same between the randomization arms. The alternative hypothesis is that infection

rates within 14 days of surgery are not equal between the randomization arms. The infection rates are assumed to be 11% in the control arm and 1% in the experimental arm based on our preliminary data. A sample size of 85 per group will give 80% power to detect a 10% difference in infection rate when the two-sided Z-test with alpha=0.05 is used. Demographics and potential confounding factors will be summarized by randomization arm. A logistic regression model will be used to measure the association between the primary outcome and treatment arm with adjustment for the observed covariates.

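### Procedure type, which the protocol itself says affects infection risk, is neither a stratum in the randomisation nor named in the primary analysis; the effect on the result is modest and a procedure-stratified test corrects it

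*Combined protocol and SAP*

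**What the plan says.** Section 8.4 is the whole allocation plan. It says "A randomization list will be generated using a computer-based-random number generator", with a 1:1 ratio and 110 per group, and that "study staff will pull an envelope after the participant signs consent". It mentions no strata and no blocks. It states that research staff are not blinded to the groups, and it does not describe the envelopes as sealed, opaque or numbered.

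Sections 4.0 and 5.0 admit ureteroscopy, PCNL and other transurethral procedures to one trial. Section 3.0, Aim 1, puts the investigators' own ureteroscopy infection rate at nearly 5-10% and says that the PCNL rate is higher, without a figure. Section 2.0 cites two separate studies of systemic inflammatory response syndrome: for ureteroscopy, "SIRS) after flexible ureteroscopic (URS) lithotripsy is 7.1" percent; for PCNL, one that "observed signs of SIRS in up to 27% of patients who underwent PCNL".

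Section 10.0 describes two analyses of the primary endpoint, infection within 14 days. The sample-size paragraph plans a logistic regression adjusted for observed covariates, none of them named. The statistical-analysis paragraph gives a plain chi-squared comparison of the arms.

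**The concern.** Procedure is a baseline factor that the protocol treats as prognostic. It is known when the patient is approached, because Section 8.1 has the patient elect the procedure first. Yet neither the allocation nor the primary test uses it. If one arm receives more PCNL patients by chance, its infection rate rises for a reason unrelated to sequencing, and the unadjusted test does not correct for that.

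The trial expects few events, so small shifts can matter near the significance boundary. Under the planning rates, 110 per arm gives 12.1 control and 1.1 experimental events. Aim 1 also states a 75% reduction, which is 11% to 2.75%, or about 12 against 3. For 12 v 3 the uncorrected test gives z = (9/110)/sqrt(2 x 0.0682 x 0.9318/110) = 2.41. For 11 v 4, with the same total, z = (7/110)/0.0340 = 1.87. The two differ by 2/110 = 1.8 points, and only the first is significant at the two-sided 5% level.

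**Working it through.** **Inputs from the documents.** Section 10.0: "The infection rates are assumed to be 11% in the control arm and 1% in the experimental arm"; "A sample size of 85 per group will give 80% power to detect a 10% difference in infection rate"; "two-sided Z-test with alpha=0.05". Section 8.4: 110 per group. Section 2.0: SIRS 7.1% (ureteroscopy) and up to 27% (PCNL).

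**Assumptions.** The PCNL share q is not given; 20-40% is used. SIRS stands in for infection, because no PCNL infection rate is given.

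**1. The plan's own figure.** n = (1.960 + 0.842)² x (0.11 x 0.89 + 0.01 x 0.99)/0.10² = 84.6, so 85 per group. The figure reproduces with unpooled variance.

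**2. Is the proxy compatible with the planned 11%?** The share that gives 11% overall is (11 - 7.1)/(27 - 7.1) = 0.196. A share near 20% fits; 30% would imply a 13.1% control rate.

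**3. Shift from chance imbalance if treatment has no effect.** The SD of the between-arm difference in PCNL share is sqrt(2q(1 - q)/110). Multiply by 1.96 and by the risk gap, 0.27 - 0.071 = 0.199.

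| PCNL share (assumed) | SD of difference in share | 95% limit of share | Shift in infection difference |
|---|---|---|---|
| 20% | 0.054 | 0.106 | 2.1 points |
| 30% | 0.062 | 0.121 | 2.4 points |
| 40% | 0.066 | 0.129 | 2.6 points |

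At 30%, 2.4 points is about 2.7 events and takes 0.121 x 110 = 13 extra PCNL patients in one arm. Three extra patients move 3 x 0.199 = 0.6 events. At 85 per arm the limits for 20% and 30% are 2.4 and 2.7 points.

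**4. Shift under the planned effect.** If risk is 11-fold lower in the experimental arm, the procedure gap there shrinks to 0.199/11. The 95% limit is 1.96 x 0.199 x sqrt(q(1 - q)/110 x (1 + 1/121)) = 1.5 points at 20% and 1.7 at 30%.

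**5. A narrower gap.** With an assumed 5% v 15% and shares of 10-50%, the 95% limit with no treatment effect is 0.8-1.3 points.

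**6. Error rate and power.** Trials were simulated with 110 per arm, the 7.1%/27% rates and simple randomisation.

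- Overall type I error of the unadjusted test: 5.1-5.3%.
- Type I error of the unadjusted test in the roughly 5% of trials with the worst imbalance: about 8-9%.
- Type I error of the procedure-stratified Mantel-Haenszel test on the same plain list: near 5%, both overall and in those worst trials.
- Power at 20% PCNL with an 11-fold reduction: 93.4% unadjusted, 94.2% stratified. In every setting tried the gain was 1 point or less.
- Stratifying the list as well as the test added at most about 0.6 points of power.

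**The case against.** The strongest reply is that simple randomisation is valid: the error rate of the unadjusted test already averages over chance imbalance, and step 6 confirms that it stays near 5%. That stands. The remaining case is conditional. A trial that turns out badly imbalanced would be analysed by a test whose error rate, given that imbalance, is too high, although the information to correct it is at hand.

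A second reply is that Section 10.0 already plans adjusted regression and a summary of confounders by arm, and Section 8.3 collects procedure history. This stands in part. The regression would deal with the problem if procedure were in it, but procedure is not named, and the statistical-analysis paragraph gives the unadjusted test.

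A third is that the risk gap is uncertain. This also stands. The two SIRS figures come from different studies, one is an upper figure, and neither is the trial's endpoint.

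A reader might go further and infer that chance imbalance could mimic or hide most of the planned effect, or that with so few events later adjustment cannot repair it and balance must be built in. The calculations support neither. The shift at the 95% limit is about a fifth to a quarter of the 10-point effect with no treatment effect, and the stratified test on the unstratified list already holds its error rate.

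**Conclusion.** The point holds in a limited form. The plan leaves a factor that it calls prognostic out of both the allocation and the stated primary test. The consequence is a shift of up to about 2.1-2.6 points at the 95% limit under no treatment effect, less under the planned effect, and a conditional type I error of about 8-9% in the worst-balanced 5% of trials. Average error and power are barely affected. These sizes rest on SIRS as a proxy for infection, a PCNL share of 20-40%, and 110 per arm. A narrower risk gap makes them smaller. The change is worth making because it costs almost nothing, not because the trial is invalid without it.

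Envelope handling should be kept apart. Envelopes pulled by unblinded staff bear on concealment and selection bias; they do not cause chance imbalance. The text does not say that envelopes are taken out of order, so this is a missing safeguard and not a demonstrated fault.

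**What to change.** In the statistical-analysis paragraph of Section 10.0, make the primary test a Mantel-Haenszel chi-squared test stratified by planned procedure (PCNL v ureteroscopy/other). Alternatively, name procedure as the covariate in the logistic regression and state that this model is the primary analysis. Keep other covariates to very few, since about 13 events are expected under the planning rates. This costs a sentence and uses data already collected.

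As a low-cost addition, stratify the Section 8.4 list by planned procedure in permuted blocks of varying size. The cost is two lists and a short amendment, and the further gain is small once the analysis is stratified. If recruitment has begun, apply it from the amendment on.

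Separately, state in Section 8.4 that envelopes are opaque, sealed, sequentially numbered and opened in order. Section 7.0 offers no ready allocation system: "A data entry system will be prepared in RedCap, Excel, or equivalent software interface for the study" concerns data entry only.

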## 1.0 STUDY SYNOPSIS

This is a randomized controlled clinical study evaluating the use of next-generation sequencing (NGS) to improve antibiotic prescribing before ureteroscopy or percutaneous nephrolithotomy. NGS will be performed on voided urine collected as routine care approximately 30 days prior to surgery. Results will be presented to ID pharmacist within 48-72 hours to help select the most appropriate antibiotics, and independently as part of routine care, surgeons will choose the antibiotic that they would use in each case, while the ID pharmacists would select their optimum choice. Pharmacists will account for site-specific antibiotic stewardship practices, allergies, medication adjustments, and C. difficile rates. Approximately 300 subjects will be randomly assigned in a 1:1 ratio to receive either NGS antibiotic recommendation or standard of care (SOC) prophylaxis prescribed treatment. All providers within the Department of Urology who perform urologic stone procedures (n=5) will also be approached in person with an information sheet. Subjects assigned to standard of care will have urine cultures sent for analysis, and the physician will choose antibiotics based on results as per usual practice. Subjects assigned to the NGS group, in addition to routine urine culture results, will have NGS urine culture results sent to an ID pharmacist, and recommendations will be shared with the physician to determine the antibiotic selection. The physician will ultimately decide the appropriate antibiotics to prescribe. Approximately 7-14 days after surgery, the research staff will conduct a telephone call to ask about any post-operative infections, complications, and any additional antibiotics that were prescribed.

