### **3.0 SPECIFIC AIMS**

#### **Specific Aim 1: To perform a randomized clinical trial investigating the use of NGS for antibiotic selection to lower post-operative infection rates over the standard of care.**

*Hypothesis: utilization of NGS for the selection of preoperative antibiotics reduces postoperative infection rates by 75%. Our baseline rate of infection was 11-15% in our pilot study and nearly 5-10% in our investigation of those ureteroscopies (not PCNL, which has a higher rate) of infections at a university hospital. We expect with the correct antibiotics that the infection rate may drop from 11% to 1% or less. The control arm will be utilized to determine if NGS may have predicted infections or high-risk groups. Retrospective databases include anywhere from 2-15% of patients will present with a postoperative infection after transurethral surgery. Current prophylaxis strategies do not always follow guidelines, and with concerns over current non-reimbursement for infectious complications, surgeons may be using more antibiotics.*

**Specific Aim 2: Accuracy of NGS and PCR compared to standard urine culture prior to transurethral procedures.** *Hypothesis: NGS can identify 50% of negative urine cultures that could harbor uropathogenic bacteria.* We anticipate a substantial number of patients have uropathogenic bacteria present yet are not detected by traditional approaches. We seek to expand our investigation on this topic in order to understand how best to interpret the results and present them to physicians. All participants will have both a standard of care urine culture and NGS testing/ID Pharmacy review for comparative analysis. Only subjects assigned to the NGS group (n=110) will have NGS urine culture results and ID Pharmacist recommendations shared with the physician to determine antibiotic selection. Operating characteristics to include sensitivity, specificity, positive, and negative predictive value will then be performed and area under the receiver operative curve calculated. We will enroll a minimum of 250 patients and 5 urology provider-participants into this study. We anticipate that 20 of the patients will have positive urine cultures and 200 will have negative cultures. Of the 200 negative cultures we anticipate that 100 (50%) will harbor uropathogenic bacteria which will be identified via NGS.

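### The randomization list holds 220 allocations, too few for the 250 completers or the roughly 300 randomised participants that the protocol states elsewhere

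*Combined protocol and SAP*

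**What the plan says.** The protocol gives several sizes for the same trial.

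- Section 8.4: "Randomization will be created 1:1, n=110 per group". The list is then turned into envelopes: "Once created, individual envelopes will be created, and study staff will pull an envelope after the participant signs consent".
- Section 3.0, Aim 2, agrees with 110 per group: "Only subjects assigned to the NGS group (n=110) will have NGS urine culture results". Its expected culture results also total 220: "We anticipate that 20 of the patients will have positive urine cultures and 200 will have negative cultures".
- The same Aim 2 paragraph sets a larger floor: "We will enroll a minimum of 250 patients and 5 urology provider-participants into this study".
- Section 8.0: "The study will enroll 250 completers (and 5 Urology provider-participants").
- Section 1.0: "Approximately 300 subjects will be randomly assigned in a 1:1 ratio".
- Section 10.0 derives 85 per group for 80% power, from infection rates of 11% and 1% and a two-sided Z-test at alpha 0.05.

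On the target effect, Aim 1 in Section 3.0 hypothesises that "utilization of NGS for the selection of preoperative antibiotics reduces postoperative infection rates by 75" per cent. A few lines later it expects a fall from 11% to 1% or lower. Section 10.0 uses 11% and 1% and credits the assumed rates to preliminary data.

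**The concern.** Section 8.4 is the operative text: staff follow it when they allocate a participant. If it is followed literally, the envelopes run out while the trial is still recruiting to the totals given in Sections 1.0 and 8.0. From then on, allocation would depend on a step that the protocol does not describe, in a trial whose research staff, by Section 8.4, are not blinded to group. The protocol also gives no single number against which to judge that recruitment is complete.

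The disagreement over the effect size is a lesser matter. A reader who takes 75% as the hypothesis and Section 10 as its sample size would credit the trial with more power for that effect than some of the stated sizes provide, and could misread a negative result.

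**Working it through.** **1. The plan's own sample size.** The inputs from Section 10.0 are 11%, 1%, two-sided alpha 0.05 and 80% power. With the unpooled two-proportion formula:

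n = (1.960 + 0.842)² × (0.11 × 0.89 + 0.01 × 0.99) / 0.10² = 84.6, so 85 per group.

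The stated figure reproduces. The pooled-variance version gives 88, a difference of method and not an error.

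**2. List length against the stated totals.**

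- List: 2 × 110 = 220.
- Aim 2 cultures: 20 + 200 = 220, so 110 per group appears deliberate and is not a single misprint.
- Against about 300 randomised: 300 − 220 = 80 short (27% of 300).
- Against 250 completers: 250 − 220 = 30 short (12% of 250), even if nobody is lost.
- 250 against 300: 1 − 250/300 = 16.7%. These two figures fit together if one is completers and the other randomised, but no attrition rate is stated.

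**3. Whether the short list harms the powered comparison.** Power for 11% versus 1%, all participants evaluable (pooled / unpooled Z-test):

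- 110 per arm: 88.3% / 89.1%
- 125 per arm: 91.9% / 92.6%
- 150 per arm: 95.8% / 96.2%

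A list of 110 per group still leaves 85 evaluable per group after a loss of 1 − 85/110 = 22.7%.

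**4. The 75% figure.** The reduction that Section 10.0 powers is 1 − 0.01/0.11 = 90.9%. A 75% reduction from the 11% planning rate gives 0.11 × 0.25 = 2.75%, a difference of 8.25 percentage points. The 2.75% is derived here; the protocol does not state it. Power for 11% versus 2.75% (pooled / unpooled):

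- 110 per arm: 67.9% / 68.8%
- 125 per arm: 73.4% / 74.3%
- 150 per arm: 80.9% / 81.7%

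Reaching 80% would need 147 (pooled) or 144 (unpooled) evaluable per arm.

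**5. Source of the 1%.** Section 2.0 describes a pilot in which physicians did not see the NGS results and analysis followed surgery. Such a pilot can inform a rate under usual care. It cannot show a rate under NGS-guided prescribing.

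**The case against.** The best defence is that the list is long enough for the trial as powered: 220 exceeds the 2 × 85 = 170 that Section 10.0 requires. This stands. A reader might infer from the mismatch that the primary comparison is underpowered, or that 85 conflicts with the larger figures. The documents support neither. The 85 is correct for its inputs, and planning to enrol more than the minimum is not a contradiction.

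A second defence concerns Aim 2. Its minimum of 250 refers to enrolment, and footnote 1 of the study calendar (Section 6.0) lets randomization take place as late as visit 2, up to 90 days after enrolment. So 250 enrolled and 220 randomised could coexist if some participants were lost in between. That softens this one conflict, although no such loss is stated. It does not help with Section 1.0, which counts people randomised, or Section 8.0, which counts completers: 220 randomised cannot yield 250 completers.

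Third, a reader might infer that Aim 1's hypothesis has no baseline, or that it is wholly absent from the sample size. That goes too far. Aim 1 itself names the fall from 11% to 1% or lower, and Section 10.0 assumes the same rates. The other infection ranges in that paragraph are context, and only the 75% is out of line. Nor do the documents support a lower power based on a continuity-corrected test, which they never mention.

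Finally, Section 10.0 already calls both rates assumed, and the credit to preliminary data may be meant for the 11% alone. What remains is an unclear attribution.

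**Conclusion.** The inconsistency is real and sits in the text that controls allocation. A list of 220 cannot supply about 300 randomised (about 80 short) or 250 completers (at least 30 short before any loss), and nothing in the protocol extends it. The conflict with Aim 2's own minimum of 250 is softer, because unstated loss before randomization could explain it.

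The consequence is that participants after number 220 have no pre-specified allocation. It is not a loss of power for the stated effect: 110 per arm gives about 88-89% for 11% versus 1%, assuming all are evaluable.

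The 75% figure is a minor, separate inconsistency within Aim 1. If it were the intended target at an 11% baseline, power would be about 68-69% at 110, 73-74% at 125 and 81-82% at 150 evaluable per arm.

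**What to change.** 1. State one number randomised and one number evaluable, with the attrition assumption that links them, identically in Sections 1.0, 3.0, 8.0, 8.4 and 10.0.
2. Generate the list and envelopes to the number randomised: at least 250, or about 300 if the synopsis governs. Clarify whether footnote 2 of the study calendar, which lets marked procedures be done again when the culture falls outside the 45-day window, applies to randomization. Randomization carries that mark, and repeats would use extra envelopes.
3. Correct Aim 2's group size and expected counts to match. If its 20:200 split is kept (an assumption), 250 × 20/220 = 22.7 gives about 23 positive and 227 negative cultures, and 300 × 20/220 = 27.3 gives about 27 and 273.
4. Either correct the 75% in Aim 1 to agree with 11% and 1%, or, if 75% is the intended target, report its power as it is at the evaluable size, without enrolling beyond the figures already stated.
5. Clarify that the preliminary data support the 11% and not the 1%.

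The cost is protocol wording and 30 to about 80 more list entries and envelopes, plus any needed if randomization can be repeated. No participants are added beyond figures already in the protocol. If the sponsor keeps the 75% target, the price is reporting power below 80% at 250 evaluable (73-74%) and only slightly above it at 300 evaluable (81-82%).
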